8.5 Study Treatment Discontinuation, Study Withdrawal, and Termination of Subjects

- If a subject discontinues study treatment or is withdrawn/terminated from the study for any reason, the study site must immediately notify the medical monitor. The date the subject is withdrawn from the study and/or study medication and the primary reason for discontinuation, regardless of if the subject withdrawn/terminated from the entire study or only from study medication, must be clearly documented on the electronic case report form (eCRF).
- If a subject discontinues study medication, he or she should be encouraged to continue in the study, and efficacy and safety procedures should be conducted as described in this protocol. These patients should continue with subsequent study visits and assessments as specified in the protocol including follow-up visits. Study treatment discontinuation does not imply withdrawal/termination from the study.
- If a subject is withdrawn or terminated from the study before completing the protocol-specified duration of treatment, safety assessments listed under Study Withdrawal/Termination visit in the Schedule of Assessments (Table 1) are to be completed at the time of withdrawal/termination (including all protocol-required laboratory tests). The patient will be followed for the duration of the follow-up period as specified in the protocol Section 10.2.4.
- Note that if a subject withdraws consent for further participation in the study, no further study assessments are to be performed unless the subject agrees to Study Withdrawal/Termination assessments.

In the event that a subject is withdrawn/terminated prematurely from the study because of a TEAE or serious TEAE, the TEAE or serious TEAE will be followed up until it resolves (returns

to normal or baseline values) or stabilizes, or until it is judged by the investigator to no longer be clinically significant. Once a subject is withdrawn from the study, the subject may not re-enter the study.

A subject may voluntarily withdraw or be withdrawn from the study at any time for reasons including, but not limited to, the following:

- AE or SAE
- Subject withdrawal of consent: at any time, a subject's participation in the study may be terminated at his/her request or on the basis of the investigator's clinical judgement. The reason for subject withdrawal will be noted on the eCRF.

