- Investigator or the Sponsor deems withdrawal necessary at any time if either one determine that it is not in the subject's best interest to continue. This includes stopping criteria (see [Section 8.5.2](#)).
- Intercurrent illness: a condition, injury, or disease unrelated to the primary diagnosis that became apparent during treatment and necessitated the subject's termination from the study
- General or specific changes in the subject's condition that renders him/her ineligible for further treatment according to the inclusion/exclusion criteria
- Subject fails to adhere to the protocol requirements (e.g., drug noncompliance, failure to return for defined number of visits)
- Lost to follow-up: the subject stopped coming for visits, and study personnel were unable to contact the subject
- Pregnancy, as indicated in [Section 12.6.6](#).
- NGT is inserted postoperatively
- Subject remains or reverts to nothing by mouth (NPO) status and is no longer able to receive oral medications

Additionally, the Sponsor could have stopped the study at any time for safety, regulatory, legal, or other reasons aligned with Good Clinical Practice (GCP). This study could have been terminated at the discretion of the Sponsor or any regulatory agency. An investigator could have elected to discontinue or stop the study at his or her study site for any reason, including safety or low enrollment.

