10 STUDY PROCEDURES

[Table 1](#) outlines the timing of procedures and assessments to be performed throughout the study. [Section 12.5](#) specifies laboratory assessment samples to be obtained. See [Section 11](#) and [Section 12](#) for additional details regarding efficacy assessments and safety assessments, respectively. Details for PK analytical methodology are presented in [Section 13](#).

Table 1. Schedule of Assessments

Procedure	Screening Day -28 to -1 ^a	Surgery Day -1		Randomization Day 1	Day 2 to 10 ^b	Hospital Discharge or Study Withdrawal/Termination	Follow- up Contact ^c	30 days (+15 days) After Discharge Follow-up Visit ^d
		Pre- surgery	Post- surgery					
Informed consent	X							
Study screening eligibility/ inclusion/exclusion criteria	X	X	X					
Randomization Eligibility Criteria				X				
Demographics, medical history, including previous abdominal surgeries	X	X						
Medication history/ concomitant medications	X ^e	X	X	X	X	X	X	X
COVID-19 screening questions ^f	X	X						
COVID-19 test	X							
Pregnancy test ^g	X	X						
Physical examination ^h	X					X		X
Vital signs ⁱ	X			X		X		X

This document is confidential.

Procedure	Screening Day -28 to -1 ^a	Surgery Day -1		Randomization Day 1	Day 2 to 10 ^b	Hospital Discharge or Study Withdrawal/Termination	Follow- up Contact ^c	30 days (+15 days) After Discharge Follow-up Visit ^d
		Pre- surgery	Post- surgery					
12-lead ECG ^j	X			X		X		
Serology ^k : HBV, HCV	X							
Hematology, serum chemistry, urinalysis ^l	X			X		X		
LFTs ^m	X	X		X	X	X		X
Record surgery start and stop time			X					
Record estimated blood loss			X					
Record need for blood transfusion			X					
Record total intraoperative IV fluid type and volume								
Record NGT removal, if used intraoperatively			X					
Record information on postoperative NGT insertion, if used				X	X	X		
Randomization				X				

Procedure	Screening Day -28 to -1 ^a	Surgery Day -1		Randomization Day 1	Day 2 to 10 ^b	Hospital Discharge or Study Withdrawal/Termination	Follow- up Contact ^c	30 days (+15 days) After Discharge Follow-up Visit ^d
		Pre- surgery	Post- surgery					
Administration of study medication TID every 6 hours ⁿ				X	X	X		
Perform GI assessments twice daily ^o				X	X	X		
Subject eDiary assessments ^p				X	X	X		
Ready for discharge based solely on GI recovery (when applicable)				X	X	X		
Hospital discharge order written						X		
Time to discontinue IV fluids and transition to oral liquids (when applicable)				X	X	X		

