10.2.1.3 Postoperative Elements

- A multimodal, opioid-sparing, pain management plan should be implemented as appropriate (e.g., combination of acetaminophen and NSAIDs).
 - Gabapentinoids (i.e., gabapentin, pregabalin) should not be used unless indicated for postoperative neuropathic pain. (See [Section 9.6.1](#))
 - **Note:** although an opioid-sparing approach should be used for postoperative pain management, opioid analgesics use is not prohibited.
- Indwelling NGTs for *prophylaxis* cannot be used.
- Protocol guidelines for selective postoperative nasogastric intubation for the management of clinical events should be followed, as shown below.
 - Occurrence of one or more of the following events:
 - ≥ 2 low-volume (e.g., < 300 cc) episodes of emesis
 - ≥ 1 high-volume (e.g., ≥ 300 cc) episode of emesis
 - Moderate to severe abdominal distension
- IV fluids are to be discontinued as soon as the subject can tolerate oral liquids and maintain adequate hydration.

- Begin oral feeding early unless otherwise contraindicated.
- Subjects must be mobilized early, starting from Day 1 unless otherwise contraindicated.
- For the purposes of this protocol, in order to reduce confounding of the effect of TU-100 on the primary outcome measure, the following interventions are prohibited:
 - Alvimopan, methylnaltrexone, naloxone (except for treatment of known or suspected opioid overdose)
 - Routine use of laxatives and stool softeners
 - Prophylactic use of prokinetics (e.g., metoclopramide, cisapride, domperidone, erythromycin used as a prokinetic agent)
 - Sham feeding (e.g., gum chewing)

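### Section 8.5 allows withdrawal from the study for postoperative NGT insertion or NPO status without saying when such subjects stay under assessment, so primary-endpoint times may be lost for reasons tied to the outcome

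*Combined protocol and SAP*

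**What the plan says.** Section 8.5 contains two routes.

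- **Stopping drug only.** The subject stays: "he or she should be encouraged to continue in the study, and efficacy and safety procedures should be conducted as described in this protocol". The section adds: "Study treatment discontinuation does not imply withdrawal/termination from the study".
- **Leaving the study.** The list opens with "A subject may voluntarily withdraw or be withdrawn from the study at any time for reasons including, but not limited to, the following" and includes "NGT is inserted postoperatively" and "Subject remains or reverts to nothing by mouth (NPO) status and is no longer able to receive oral medications". Withdrawal is final: "Once a subject is withdrawn from the study, the subject may not re-enter the study".

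Other sections bear on what is then collected.

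- Table 1 has a row, "Record information on postoperative NGT insertion, if used", marked for Day 1, Days 2 to 10 and discharge or withdrawal.
- The termination visit (Section 10.2.3) includes a GI assessment. After that, GI assessments (11.2) and investigator review of the eDiary (11.3) end.
- Follow-up under 10.2.4 covers complications and readmission but no GIR times. With 11.7, only coarse information remains: prolonged ileus at Day 3 or 5, recurrent ileus and readmission.
- Section 10.2.1.3 ties NGT insertion to clinical events ("Protocol guidelines for selective postoperative nasogastric intubation for the management of clinical events should be followed, as shown below"), namely emesis or moderate to severe distension. Section 6.2.2 makes NGT insertion for ileus symptoms part of a secondary endpoint.
- Section 14.3 keeps a subject in the FAS with one GIR assessment. The only censoring rule given for time to GIR (TGIR) is at 240 hours (14.5.2). Detailed missing-data rules (14.4) and TGIR sensitivity analyses (14.5.2) are deferred to a SAP, whose text is not part of the document reviewed.

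**The concern.** The primary objective is resolution of postoperative ileus, and subjects who need an NGT or revert to NPO are those in whom ileus is clinically evident. If a site uses the withdrawal list, their recovery times are missing because recovery is slow. A Cox model that censors at withdrawal treats them as if they would recover at the same rate as subjects still at risk in their arm. That can distort the hazard ratio and the power, in a direction that depends on the NGT rate in each arm and on any drug effect after NGT.

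Sites may also read the list differently, so the extent of loss would be arbitrary. A later SAP can choose a rule for these subjects, but it cannot recover times that were never recorded. The extra 36 subjects in Section 14.2 replace lost events. They do not correct for loss that depends on outcome.

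**Working it through.** **1. The plan's own figure.** Section 14.2 gives HR 1.428, one-sided 0.05, and 366 subjects before inflation, so 122 per arm and 244 in a pairwise comparison. If all have the event, Schoenfeld's formula gives z = √(244 × 0.25) × ln 1.428 − 1.645 = 7.810 × 0.3563 − 1.645 = 1.138, a power of 87.2%. The stated 87% reproduces.

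**2. Non-informative loss.** With 134 per arm (268 pairwise), losing 10% leaves 268 × 0.90 = 241 events and 86.9% power. The 36 extra subjects therefore cover about a 10% loss, provided the loss is unrelated to outcome.

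**3. Informative loss: illustration only.** NGT rate, timing, later recovery and any drug effect after NGT are all assumptions.

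- 134 per arm; Cox model with a treatment term, Breslow ties, one-sided 0.05 Wald test, administrative censoring at 240 h; 20,000 trials per scenario (Monte Carlo error of power at most 0.35 points).
- Base inputs: exponential GIR with placebo median 48 h (14.2) and HR 1.428 in subjects without NGT. NGT falls uniformly at 24 to 96 h, always before GIR, with placebo median 96 h from NGT to GIR.
- Without any NGT the model returns HR 1.43 and 89% power. This exceeds 87% because it uses 134 per arm, not 122.

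Followed to GIR versus all NGT subjects censored at NGT, base inputs (a dash means only the change is reported):

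| NGT placebo / TU-100 | Drug effect after NGT | HR followed | HR censored | Change in HR | Change in power (points) |
|---|---|---|---|---|---|
| 2% / 2% | persists | – | – | +0.01 | +1 |
| 5% / 5% | persists | 1.393 | 1.416 | +0.02 | +2 |
| 10% / 10% | persists | 1.368 | 1.402 | +0.03 | +2 |
| 10% / 7% | persists | 1.443 | 1.454 | +0.01 | −1 |
| 2% / 2% | none | – | – | +0.03 | +3 |
| 5% / 5% | none | 1.358 | 1.416 | +0.06 | +7 |
| 10% / 10% | none | 1.304 | 1.400 | +0.10 | +14 |
| 10% / 7% | none | – | – | +0.06 | +5 |
| 10% / 20% | persists | 1.16 | 1.23 | +0.07 | +11 (33% to 44%) |
| 10% / 20% | none | 1.08 | 1.23 | +0.15 | +29 (15% to 44%) |

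5% to 10% of 134 is about 7 to 13 subjects per arm.

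**4. Other inputs.** Set 2 shortens the median from NGT to GIR to 48 h. Set 3 starts the clock at entry 14 to 28 h after surgery, with placebo median 28 h from entry, NGT at 30 to 96 h, and GIR 48 to 120 h after NGT. Over the three sets, at equal rates of 5% to 10%:

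- All withdrawn: −0.005 to +0.07 in HR (−4 to +9 points of power) if the effect persists; +0.03 to +0.10 (+2.5 to +16 points) if it does not.
- Half withdrawn: −0.002 to +0.025 (−2 to +3 points); +0.01 to +0.04 (+1 to +6 points).

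The direction can reverse. In set 2 with a persisting effect and 10% / 20%, censoring lowers HR from 1.265 to 1.225 (power 59% to 44%).

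**5. No drug effect on GIR.** At 10% / 10% the HR is 1.00 with about 5% rejections whichever way these subjects are handled. If only the NGT rate differs (placebo 20%, TU-100 10%), HR is 1.15 followed, 1.11 censored and 1.28 if set event-free to 240 h.

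**6. An extreme case.** Suppose the slowest 5%, 10% or 15% of each arm are censored at 48 h (2,000 trials each). A true HR of 1.428 becomes 1.53, 1.60 or 1.62. With no drug effect the mean HR stays at 1.00, but one-sided rejections rise to 13% to 18%. The 5% in step 5 therefore belongs to that model and is not general.

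**The case against.** The strongest reply is that the text already works. The list is permissive, 8.5 distinguishes stopping drug from leaving the study, and the NPO item turns on being unable to take oral medication, which is a dosing matter. A careful site would keep such a subject under assessment. That reading is reasonable, but no sentence assigns NGT or NPO subjects to it, and both items stand in the study-withdrawal list.

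Second, censoring at withdrawal is an inference, since the text gives no such rule and the SAP could set another. This stands as a limit on the claim. It does not remove the loss of data, and the choice matters: at 10% / 10% with no effect after NGT, power is about 83% if censored and 54% if event-free to 240 h.

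Third, where the drug effect ends at NGT, following subjects dilutes the HR, so the gap is partly a difference in estimand. It is a bias only against a treatment-policy target. The plan points that way, since the FAS is analysed as randomised and 8.5 asks for efficacy data after drug is stopped, but it never states an estimand.

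Fourth, some NGTs will follow GIR, because upper recovery is only the step beyond clear liquids. With NGT times drawn independently of GIR in the base case, 38% preceded GIR. At NGT rates of 5% and 10% the shift fell to about +0.02 and +0.03 with no later effect, and below +0.01 with a persisting one. So 7 to 13 per arm is the upper reading of a 5% to 10% NGT rate.

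**Conclusion.** The concern holds as a gap in the plan. Section 8.5 makes outcome-related loss of the primary endpoint possible without directing it, and what is lost cannot be recovered later.

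A large bias is not shown. The size is unknown because no NGT or NPO rate, timing or withdrawal share is given. Under the illustrative inputs with equal rates of 5% to 10%, the shift runs from about zero to +0.10 in HR. It is larger if rates differ between arms, and its sign can change. These figures assume every counted NGT precedes GIR and, unless half is stated, that every such subject is withdrawn and censored.

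It should be fixed because prevention is cheap. Confidence is medium.

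**What to change.** - **Section 8.5.** Reconcile the withdrawal list with the bullet on stopping drug, so that subjects with NGT insertion or NPO status remain in the study for data collection unless they withdraw consent. Continue GI assessments and eDiary review to GIR, discharge or 240 h. Dosing and the clinical management of NGT and NPO are not touched.
- **Section 14.5.2.** Use the observed GIR time in the primary analysis and state the rule for subjects whose GIR is never observed. Prespecify two sensitivity analyses: censored at withdrawal, and event-free to 240 h.
- **Reporting.** Give by arm the number withdrawn for NGT or NPO before GIR.

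The sensitivity analyses do not replace the data, because they need not bracket the followed value. In set 2 with no drug effect and placebo 20% / TU-100 10%, the HR is 1.09 followed, against 1.11 and 1.28 in the two analyses.

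The cost is one clarified list, some added wording, and continued assessment of subjects who are mostly still inpatients. The result may be less favourable than with censoring. At 5% / 5% with base inputs and all otherwise withdrawn, power goes from 86% to 84% if the effect persists after NGT and from 86% to 79% if it does not. With faster recovery after NGT and a persisting effect it rises instead, from 82% to 86% at 10% / 10%.

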8.5.1 Close Observation and Clinical Management Plan

If early signs of possible DILI are detected in a subject, close observation should be initiated, and Sponsor should be notified within 24 hours (See protocol [Section 12.6.8](#)).

Clinical signs and symptoms of possible DILI or severe hepatotoxicity that may trigger close observation include, but are not limited to, the following:

- Persistent fatigue, weakness, nausea/vomiting, anorexia, pruritis, vague abdominal pain or right upper quadrant pain or tenderness, fever, rash, eosinophilia (eosinophils > 5%) in the absence of more likely causes
- Peripheral edema, ascites, encephalopathy, GI bleeding

- ALT > 3-fold ULN in subjects with normal baseline levels or 2-fold increases above baseline in subjects with abnormal levels prior to drug exposure

Close observation includes:

- Repeating liver enzyme and serum bilirubin tests 2 or 3 times weekly (the initial retest will occur within 48 hours). Frequency of retesting can decrease to once a week or less if abnormalities stabilize or the study drug has been discontinued and the subject is asymptomatic.
- Obtaining a more detailed history of symptoms and prior or concurrent diseases
- Obtaining a history of concomitant drug use (including nonprescription medications and herbal and dietary supplement preparations), alcohol use, recreational drug use, and special diets
- Ruling out acute viral hepatitis types A, B, C, D, and E; autoimmune or alcoholic hepatitis; NASH; hypoxic/ischemic hepatopathy; and biliary tract disease
- Obtaining a history of exposure to environmental chemical agents
- Obtaining additional tests to evaluate liver function, as appropriate (e.g., INR, direct bilirubin)
- Considering gastroenterology or hepatology consultations

Note that if additional testing is conducted, this information should be recorded in the eCRF.

Note: for any subject in whom a concern for hepatotoxicity or DILI develops (i.e., any subject that meets criteria for close observation), a narrative summary will be provided to the chairman of the DSMB by the Sponsor (via the CRO DSMB manager) for review by the board. The initial narrative summary will be provided within 24 to 48 hours of Sponsor notification of identifying a subject that meets the close observation criteria and updated versions provided as additional information becomes available and/or is requested by the DSMB chairman.

Contents of the narrative summary will be comparable to the information provided in each case submitted to the CEAC for review/adjudication. Tsumura will be responsible for collecting the information and developing the narrative summary for submission to the DSMB. Based on their findings, the DSMB will make recommendations to the Sponsor regarding management of the case at the patient, site, and/or study level(s) based on their responsibilities as defined in their charter (e.g., study drug continuation, additional clinical and/or diagnostic information/testing, need for medical specialty consultation [e.g., gastroenterology/hepatology]).

Note: if transaminase elevations persist, subjects will be evaluated for other causes of transaminase elevations including tests of hepatic function (e.g., viral hepatitis, nonalcoholic fatty liver disease/NASH, ischemic hepatitis, thyroid disorders, occult celiac disease). The type and extent of testing will be determined via recommendations by the DSMB and PI (to include recommendations from clinical consults should they be performed). This may include, but is not limited to, diagnostic imaging procedures and liver biopsy. Recommended testing will be shared with the Sponsor's medical director.

If no other cause for persistent transaminase elevation is found, then the subject will be monitored closely, and the study drug will be discontinued.

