8.5.2 Stopping Criteria

Stopping criteria for subject with elevated liver tests and relevant clinical signs and symptoms:

- ALT or AST $> 8 \times$ ULN
- ALT or AST $> 5 \times$ ULN for more than 2 weeks
- ALT or AST $> 3 \times$ ULN and total bilirubin $> 2 \times$ ULN or INR > 1.5
- ALT or AST $> 3 \times$ ULN with the appearance of fatigue, nausea, vomiting, right upper quadrant pain or tenderness, fever, rash, and/or eosinophilia (eosinophils $> 5\%$)

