- ^m Samples for routine clinical liver function tests will include alkaline phosphatase, aspartate transaminase, alanine transaminase, total and direct bilirubin, prothrombin time and INR. If these tests have been performed within 28 days before surgery, but before consent is obtained, the LFTs need not be repeated unless deemed appropriate by the investigator. On Day-1 LFT do not have to be repeated if done within 14 days of Surgery and the LFT were within normal limits. On Day 1, this should be taken before study drug administration to represent baseline values. Liver functions tests to include PT/INR and will be obtained during screening, pre-surgery, Randomization Day 1, Day 4, Day 7, and Day 10 (if remaining in the hospital), and the day of hospital discharge. Liver function tests are needed at the 30-day follow-up visit only if LFTs were elevated at discharge and trending down. If a subject remains in the hospital for an AE of elevated tests, then levels will be followed until resolution. A local laboratory should be used for screening and before pre-surgery Day -1. A central laboratory should be used after randomization on Day 1 and future visits.
- ⁿ Subjects will be randomized 1:1:1 (TU-100 15 g: TU-100 7.5 g: placebo) and stratified by surgical approach (open versus laparoscopic). Study drug will be administered TID (3 times per day [i.e., 6 hours ± 1 hour apart]).

- ^o GI assessments are to be performed twice daily, morning and afternoon with assessments separated by at least 6 hours.
- ^p Subjects will record the following items in their eDiaries on all postoperative in-hospital study days: first flatus (record in real time), first BM (record in real time), nausea occurrence and bothersomeness (24-hour reflection), vomiting/retching occurrence/number of episodes (24-hour reflection), abdominal bloating occurrence and bothersomeness (24-hour reflection).
- ^q Blinded review and assessment of hepatobiliary AEs by an independent CEAC will be performed on an ongoing basis during the conduct of the study.
- ^r PK samples will be drawn only at designated sites at the following times below, and at early termination (not needed at hospital discharge). If a subject is terminating early on a day scheduled for a blood draw, a second sample on the day of termination should be taken if possible. If a subject is terminating early on a day not scheduled for a blood draw, at least 1 sample should be obtained that day if possible.

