12.6.8 Subjects Who Meet Close Observation Criteria Reporting

If a subject meets the criteria for close observation based early signs of potential DILI or hepatotoxicity (See protocol [Section 8.5.1](#)) from the day of randomization, during the study, and up to 30 days + 15 days after discharge, this must be reported to the Sponsor. This must be reported within 24 hours of occurrence or when the investigator becomes aware of the subject meeting close observation criteria.

Notifications can be made using the dedicated email address for potential DILI reporting:

[contact]

When reporting a subject who meets close observation criteria reporting to the dedicated email, the site should include the key clinical signs and symptoms of possible DILI or severe hepatotoxicity that triggered close observation, as appropriate. **Note:** clinical signs and symptoms may include, but are not limited to, the following (also See [Section 8.5.1](#)):

- Persistent fatigue, weakness, nausea/vomiting, anorexia, pruritis, vague abdominal pain or right upper quadrant pain or tenderness, fever, rash, eosinophilia (eosinophils > 5%) in the absence of more likely causes
- Peripheral edema, ascites, encephalopathy, GI bleeding
- ALT > 3-fold ULN in subjects with normal baseline levels or 2-fold increases above baseline in subjects with abnormal levels prior to drug exposure

The Sponsor will create narrative summary and will contact the site to obtain relevant information for this summary. The Sponsor will provide the narrative summary to the DSMB.

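### The listed close-observation triggers do not contain the hepatic stopping criteria: the enzyme trigger names ALT only and, above a Day 1 ALT of 1.5 x ULN, sits higher than the conditional 3 x ULN stopping level

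*Combined protocol and SAP*

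**What the plan says.** **Triggers.** Section 8.5.1 opens with a general duty: "If early signs of possible DILI are detected in a subject, close observation should be initiated, and Sponsor should be notified within 24 hours". It then lists signs and symptoms "that may trigger close observation include, but are not limited to, the following". The list has two clinical bullets and one enzyme bullet: "ALT > 3-fold ULN in subjects with normal baseline levels or 2-fold increases above baseline in subjects with abnormal levels prior to drug exposure". Section 12.6.8 repeats the list for reporting. No listed trigger names AST, bilirubin or INR.

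**What the triggers set off.** Close observation includes repeat liver tests, and "the initial retest will occur within 48 hours". For reporting, Section 12.6.8 says: "This must be reported within 24 hours of occurrence or when the investigator becomes aware of the subject meeting close observation criteria". The sponsor then sends a narrative to the DSMB chair within 24 to 48 hours of being notified. Section 8.5.1 defines the subjects concerned as "any subject that meets criteria for close observation".

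**Stopping.** Section 8.5.2 is introduced as "Stopping criteria for subject with elevated liver tests and relevant clinical signs and symptoms". Its four criteria all refer to ALT or AST: above 8 x ULN; above 5 x ULN for more than 2 weeks; above 3 x ULN with total bilirubin above 2 x ULN or INR above 1.5; and above 3 x ULN with listed symptoms. The Hy's law summary in Section 14.6.4 also uses either enzyme.

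**Baseline.** Table 1, footnote m, says of the liver tests: "On Day 1, this should be taken before study drug administration to represent baseline values". The baseline is therefore a postoperative, pre-dose value.

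**The concern.** In a graded liver-safety scheme, the level that starts closer watching should be reached no later than the level that stops the drug. Here the watching list is narrower than the stopping list in one respect (enzyme) and can be higher in another (baseline-relative threshold).

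The prompt actions are all tied to the close-observation criteria, and no visible text ties them to Section 8.5.2. A subject can therefore meet a stopping criterion, including the Hy's law pattern, while the 48-hour retest, the 24-hour DILI report and the DSMB narrative depend on how the site reads an open list. Up to about 55 sites will be reading it. Without the narrative, the DSMB route that Section 14.10 describes is review of periodic safety data cuts.

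Evaluating DILI risk is a stated purpose of the trial (Section 5.4), and hepatobiliary events are a secondary objective (Section 6.1.2). Sample size and efficacy analysis are not affected.

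**Working it through.** The plan states no figure on this point, so there is nothing to reproduce. The check compares the two lists in multiples of ULN.

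**Inputs.** Trigger: Sections 8.5.1 and 12.6.8. Stopping levels: Section 8.5.2. Baseline: Table 1, footnote m, and Section 14.1 (last value before first dose).

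**Enzyme.** With a normal baseline the listed trigger is ALT > 3. The stopping criteria apply to the higher of ALT and AST. Whenever ALT ≤ 3 and AST > 3, the enzyme trigger is silent while a stopping criterion may be met.

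**Baseline.** Let b be Day 1 ALT in multiples of ULN, with b > 1. Reading the wording as twice baseline, the trigger is 2b.

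- 2b = 3 at b = 3/2 = 1.5. Above that, the trigger exceeds the conditional 3 x ULN level.
- 2b = 8 at b = 8/2 = 4. Only above that does it exceed the 8 x ULN criterion.
- For b between 1 and 1.5 the trigger is below 3 x ULN (b = 1.1 gives 2.2), so there is no inversion.

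The text does not say whether exactly twice baseline counts. That does not move these crossings. If the wording instead means a rise of twice baseline, the trigger is 3b, and the crossings fall to b > 1 and b > 8/3 = 2.67.

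**Cases**, all without a symptom trigger, under the 2b reading:

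| Baseline ALT | On treatment (x ULN) | Stopping criterion met? | Listed enzyme trigger met? |
|---|---|---|---|
| normal | AST 3.5, ALT 2.5, bilirubin 2.5 | yes (third); also Hy's law in 14.6.4 | no (ALT 2.5 ≤ 3) |
| normal | AST 8.5, ALT 2.5 | yes (first) | no (ALT 2.5 ≤ 3) |
| 2 | ALT 3.5, bilirubin 2.5 | yes (third) | no (3.5 < 2 × 2 = 4) |
| 1.2 | ALT 3.5, bilirubin 2.5 | yes (third) | yes (3.5 > 2 × 1.2 = 2.4) |
| normal | ALT 3.5, bilirubin 2.5 | yes (third) | yes (3.5 > 3) |

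The last two rows show the limits of the gap. With a normal or mildly raised baseline, an ALT-based stop meets the trigger. The first two rows show that the AST gap needs no abnormal baseline.

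**Symptoms.** The symptom bullet overlaps the fourth stopping criterion but does not contain it. It asks for persistent fatigue and discounts symptoms that have a likelier explanation, which after bowel surgery can cover nausea, vomiting or fever. The fourth stopping criterion carries neither limit.

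**The case against.** **Notification.** A reader might infer that an AST-led stopping case would go unreported. The documents do not support that. Section 8.5 requires the site to tell the medical monitor immediately when treatment stops or a subject is withdrawn for any reason, and it names the stopping criteria among the grounds for withdrawal. Sections 8.3.1 and 9.3.2 identify this as the sponsor's medical monitor, and the sponsor writes the narrative. Withdrawn subjects also have termination liver tests and follow-up. This stands. What it does not supply is a 48-hour retest or a DSMB narrative.

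**Open list.** The duty in Section 8.5.1 covers early signs of possible DILI in general, and Section 6.2.3 has retests of AST, ALT and bilirubin. Few investigators would regard a Hy's law pattern as outside that. This also stands: nothing forbids close observation for AST. But a lone ALT rise is listed, while some more serious patterns are left to judgement.

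**Other safety nets.** Section 8.5.1 adds a work-up if elevations persist, Section 12.5 follows clinically significant values, and the adjudication committee and Section 14.6.4 still count cases.

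**Abnormal baselines.** Exclusion 19 bars ALT or AST above ULN, and Section 8 asks that screening eligibility hold after surgery as well. This may make a Day 1 ALT above 1.5 x ULN uncommon. It does not rule it out: Section 8.4 has no liver criterion, and the trigger itself provides for abnormal pre-dose levels.

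**Heading of 8.5.2.** It can be read as requiring symptoms for every criterion. The enzyme-only cases might then not be stopping cases, and more of the rest would meet the symptom bullet. The overlap would still be incomplete, for the reasons given above.

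**Unseen text.** Section 12.6.2, on adverse events of special interest, appears only as a heading in the text available, and the DSMB and adjudication charters are separate documents. Any of these could hold the missing link.

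**Conclusion.** The point holds as an inconsistency between two lists. The listed enzyme trigger is narrower than the stopping criteria because it omits AST. It can also be higher than the conditional 3 x ULN level when Day 1 ALT exceeds 1.5 x ULN, taking the baseline-relative wording as twice baseline. Two things remain after the safeguards are counted: no visible text ties the 48-hour retest or the 24-to-48-hour DSMB narrative to an 8.5.2 criterion, and isolated AST above 3 x ULN has no listed enzyme trigger.

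It would go too far to say that stopping cases escape detection or the sponsor's notice, or that every abnormal baseline inverts the scheme. The documents give no frequency for AST-led rises or for abnormal Day 1 tests, so no patient count can be stated.

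Confidence is high that the lists do not nest. It is medium on the consequence, because Section 12.6.2 and the charters are not visible. This is a cheap improvement to safety monitoring, not a flaw in the trial's main inference.

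**What to change.** Make two changes, each in both Section 8.5.1 and Section 12.6.8.

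1. Add: *Meeting any Section 8.5.2 criterion also counts as meeting the close-observation and reporting criteria.* This captures every stopping case by definition, whatever the baseline and however the 8.5.2 heading or the 2-fold wording is read.
2. In the enzyme trigger, change ALT to ALT or AST. At normal baseline this gives isolated AST above 3 x ULN a listed trigger before it becomes a stopping case.

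The baseline-relative threshold can otherwise stay.

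The cost is one sentence and two added words in each place, with no new scheduled sample or visit and no change to sample size or analysis. The downside is some additional retests, 24-hour reports and DSMB narratives. Their number cannot be estimated from the documents.
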